6.4.2 Analysis of Secondary Efficacy Endpoints

6.4.2.1 Clinical Benefit Rate

CBR is defined as the proportion of subjects for each dose level whose best overall response is rated as confirmed CR, PR or durable SD. Durable SD is a SD maintained for at least 12 weeks. CBR by dose level will be calculated and its 90% confidence interval will be constructed

6.4.2.2 Duration of Response

DOR will be calculated only for the subgroup with confirmed response CR/PR. The distribution of DOR will be estimated for phase 2 subjects only using Kaplan-Meier methodology.

6.4.2.3 Progression-Free Survival

PFS is defined as the time from the date of first dose until the date of disease progression, or until death due to any cause. If a subject has neither progressed nor died, the subject will be censored at the date of last disease assessment or at the date of registration if no post-baseline radiological assessment is available. Subjects who receive any further anticancer therapy for the disease before radiological progression will be censored at the date of the last radiological assessment before the anticancer therapy started. If progression or death occurs after missing 2 scheduled radiological assessments, the subject will be censored at the date of last radiological assessment or at the date of registration if no post-baseline radiological assessment is available. A subject has missed 2 scheduled disease assessments if the gap between two disease assessments is more than 2.5 times the scheduled disease assessment interval. During treatment, this will be 105 days (2.5 x 42 days during treatment for the first 24 weeks); during the follow-up period this will be 210 days (2.5 x 84 days during follow-up).

PFS will be derived for phase 2 subjects only. The distribution of PFS will be estimated for each dose level using Kaplan-Meier methodology.

PFS (in days) is calculated as:

(Date of death or documented Progression or censoring) – (Date of first dose date) +1.

To apply the cut-off date to PFS is to exclude tumor assessments, death and anti-cancer therapy date after cut-off date in the analysis.

Note: Patient cannot be censored at “Not Evaluable (NE)”. If NE is the only previous assessment, then PFS will be censored at Day 1.

6.4.2.4 β hCG and AFP

Levels of β hCG and AFP, as well as change from baseline, during the study will be tabulated and presented in line charts for FAS and SAF.

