5 EFFICACY AND SAFETY ENDPOINTS

5.1 Primary Efficacy Endpoints

5.1.1 Objective Response Rate

ORR is defined as the proportion of subjects who have a best overall response of confirmed CR or confirmed PR, as assessed by modified RECIST 1.1. A response of CR or PR must be maintained for at least 4 weeks to be confirmed.

For subjects with measurable disease at baseline, the following criteria in [Table 1](#) will be used to assess response using modified RECIST 1.1:

Table 1 Response Criteria Based on Modified RECIST v1.1

Serum Markers	Target Lesions	Non-Target Lesions	New Lesions	Overall Timepoint Response Assessment	
	(target lesion response)	(non-target lesion response)	(unequivocal new lesions)		
Values that fall below the ULN for the assay employed	CR	CR	No or Equivocal	CR	
	CR	Not Applicable	No or Equivocal	CR	
	Not applicable	CR	No or Equivocal	CR	
For both AFP and beta-hCG, no increase \geq 50% in 2 samples at least 1 week apart compared to nadir values, at least one of the values are above ULN	CR	CR	No or Equivocal	PR	
	CR	Not Applicable	No or Equivocal	PR	
	Not applicable	CR	No or Equivocal	PR	
For both AFP and beta-hCG, no increase \geq 50% in 2 samples at least 1 week apart compared to nadir values	CR	Non-CR/Non-PD	No or Equivocal	PR	
	CR	NE/ND	No or Equivocal	PR	
	PR	CR	} = not PD	No or Equivocal	PR
	PR	Non-CR/Non-PD		No or Equivocal	PR
	PR	NE/ND	No or Equivocal	PR	
	PR	Not applicable	No or Equivocal	PR	
For both AFP and beta-hCG, no increase \geq 50% in 2 samples at least 1 week apart compared to nadir values	SD	CR	} = not PD	No or Equivocal	SD
	SD	Non-CR/Non-PD		No or Equivocal	SD
	SD	NE/ND		No or Equivocal	SD
	SD	Not applicable		No or Equivocal	SD
Any	PD	Any	Any	PD	
Any	Any	PD	Any	PD	
Any	Any	Any	Yes or Unequivocal	PD	
Increase \geq 50% in serum tumor markers AFP or beta-hCG in 2 samples at least 1 week apart compared to nadir values	Any	Any	Any	PD	
NE/ND	NE/ND	Not PD	No or Equivocal	NE	

CR: complete response; ND: not done; NE: non-evaluable; PD: progressive disease; PR: partial response; SD: stable disease.

Confirmatory assessment for CR or PR should be done at least 4 weeks after the date of the CR or PR was first observed.

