5.2.3 Progression-Free Survival (PFS)

PFS is defined as the time from the date of first dose until the date of disease progression as assessed by modified RECIST 1.1, or until death due to any cause. If a subject has neither progressed nor died, the subject will be censored at the date of last disease assessment or at the date of registration if no post-baseline radiological assessment is available. Subjects who receive any further anticancer therapy for the disease before disease progression will be censored at the date of the last disease assessment before the anticancer therapy started. If progression or death occurs after missing 2 scheduled disease assessments, the subject will be censored at the date of last disease assessment or at the date of registration if no post-baseline disease assessment is available. A subject has missed 2 scheduled disease assessments if the gap between two disease assessments is more than 2.5 times the scheduled disease assessment interval. During treatment, this will be 105 days (2.5 x 42 days during treatment for the first 24 weeks); during the follow-up period this will be 210 days (2.5 x 84 days during follow-up).

PFS (in days) is calculated as:

(Date of death, or Progression assessed by modified RECIST 1.1, or censoring) – (Date of first dose) +1.

To apply the cut-off date to PFS is to exclude disease assessments, death and anti-cancer therapy date after cut-off date in the analysis.

Note: Patient cannot be censored at “Not Evaluable (NE)”. If NE is the only previous assessment, then PFS will be censored at Day 1.

PFS will be calculated for each subject using RECIST 1.1 alone, and serum markers alone.

Table 3 PFS Definition

Situation	Date of Event or Censor	Outcome
No evaluable post-baseline efficacy assessments, no death	Date of first dose	Censor
Subject did not receive new anti-cancer therapy:		
Disease progression documented per modified RECIST v1.1	Date of PD	Event
No disease progression, but death recorded on eCRF	Date of death	Event
No PD nor death	Date of last efficacy assessment or at the date of first dose if no postbaseline efficacy assessment is available	Censor
Subject received new anti-cancer (ACT) therapy:		
Disease progression documented per modified RECIST v1.1 after new ACT	Date of last efficacy assessment before start of new anti-cancer therapy or at the date of first dose if no post-baseline efficacy assessment is available	Censor

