Disease progression documented per modified RECIST v1.1 before new ACT	Date of PD	Event
No disease progression before new ACT but death recorded	Date of last efficacy assessment before start of new anti-cancer therapy or at the date of first dose if no post-baseline radiological assessment is available	Censor
No disease progression nor death	Date of last efficacy assessment before start of new anti-cancer therapy or at the date of first dose if no post-baseline efficacy assessment is available	Censor
Missed 2 scheduled efficacy assessments:		
If disease progression or death occurs after missing 2 scheduled efficacy assessments	Date of last efficacy assessment or at the date of first dose if no postbaseline efficacy assessment is available	Censor

PFS = Date of Event or Censor – Date of First Dose +1

PFS by RECIST1.1 will be also be derived as described in [Table 3](#).

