7 REVISION AND RATIONALE

Version	Date	Changes	Comment/rationale for change
1.0	02Nov2018	started	
2.0	10Feb2021	updated	clarified blood draw schedule for post treatment period; allowed cohort 2 and beyond to have up to 4 subjects derivation of PFS inaccurately had noted registration date as first date; clarified to be first dose date Updated to align with protocol version 3.1 incorporating Nonsubstantial Amendment 1 Updated to describe biomarker analysis

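### SAP 6.4.2.3 and SAP 5.2.3/Table 3 give conflicting PFS censoring rules, so a subject with marker progression who then starts new therapy is censored under one and an event under the other

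*SAP*

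**What the plan says.** Protocol 7.4.2.3 leaves the detailed PFS censoring algorithm to the SAP. The SAP gives it twice.

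- **SAP 5.2.3** names the criterion: "PFS is defined as the time from the date of first dose until the date of disease progression as assessed by modified RECIST 1.1", or death. On new therapy it says: "Subjects who receive any further anticancer therapy for the disease before disease progression will be censored at the date of the last disease assessment" before that therapy. Its Table 3 has a row, "Disease progression documented per modified RECIST v1.1 before new ACT", whose outcome is an event on the date of PD.
- **SAP 6.4.2.3** names no criterion: "PFS is defined as the time from the date of first dose until the date of disease progression, or until death due to any cause". On new therapy it says: "Subjects who receive any further anticancer therapy for the disease before radiological progression will be censored at the date of the last radiological assessment" before that therapy. Its missed-visit rule counts radiological assessments, where 5.2.3 counts disease assessments.
- **SAP 5.1.1, Table 1** makes a rise of at least 50% "in serum tumor markers AFP or beta-hCG in 2 samples at least 1 week apart compared to nadir values" PD, with any lesion status.
- **Fallback date.** With no post-baseline assessment, the text of 5.2.3 censors "at the date of registration if no post-baseline radiological assessment is available". The text of 6.4.2.3 has the same fallback. Table 3 uses the date of first dose.
- **SAP 7** records: "derivation of PFS inaccurately had noted registration date as first date; clarified to be first dose date".

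**The concern.** Two rules for one endpoint, with no statement of which prevails, leave the choice to whoever programs the analysis, in an open-label trial. The choice matters because the sequence that separates the rules can readily occur. Protocol 6.1 makes marker progression a reason to stop treatment. Markers are drawn every 14-day cycle and scans are taken every 6 weeks, so marker progression can come before the first scan. Imaging stops once other systemic anticancer treatment starts (Protocol 5.3.1.1), so the protocol scans would not later supply a radiological progression date. Subjects whose only evidence of disease is a rising marker are eligible (inclusion criterion 11). For them, a rule tied to radiological progression would normally miss the progression that the trial is set up to detect.

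Subjects censored this way have just progressed by the trial's own criterion. Such censoring is informative, and in a single-arm trial no comparator offsets it.

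**Working it through.** **1. The plan's own figures.** The missed-assessment gap is 2.5 × 42 = 105 days in the first 24 weeks and 2.5 × 84 = 210 days in follow-up. Both reproduce and are the same in 5.2.3 and 6.4.2.3. Only the type of assessment counted differs.

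**2. One subject under both rules.** Formula (both sections): date of event or censoring − date of first dose + 1. Markers are at least 50% above baseline (the nadir) at C2D1 (day 15) and C3D1 (day 29), which are 14 days apart. PD is dated at the second sample. The first scan is due on days 43 to 50 (6 weeks + 7 days). New therapy starts before it.

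| Rule | Outcome |
|---|---|
| 5.2.3 / Table 3 | Event, PFS = 29 days |
| 6.4.2.3 new-therapy sentence | Censored, with no post-baseline scan to censor at |

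**3. What this does to the curve.** Suppose k of 34 subjects follow this path and no other subject has an event before day 43. PFS at day 42 under Table 3 is 1 − k/34. Under 6.4.2.3 there is no event by day 42, so the estimate is 100%. If all 34 eventually have events under Table 3, 6.4.2.3 leaves 34 − k.

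| k | PFS at day 42, Table 3 | PFS at day 42, 6.4.2.3 | Events, 6.4.2.3 |
|---|---|---|---|
| 3 | 91% | 100% | 31 |
| 7 | 79% | 100% | 27 |
| 10 | 71% | 100% | 24 |
| 17 | 50% | 100% | 17 |

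The documents do not give k.

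**4. Effect on the median (illustration only).** Assumptions: 34 subjects, exponential PFS with true median 8 weeks, markers every 2 weeks, scans every 6 weeks, a share f of events being marker PD followed by new therapy, 3,000 simulated trials. Mean Kaplan-Meier median:

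| f | Event rule | Censor rule |
|---|---|---|
| 20% | 10.7 weeks | 12.8 weeks |
| 30% | 10.5 weeks | 13.9 weeks |
| 40% | 10.2 weeks | 15.6 weeks |

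The event rule exceeds 8 weeks largely because progression is seen only at visits. The relevant contrast is between the two columns.

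**5. Check by formula.** If only the event count fell, an exponential median would rise by 1/(1 − f): +25% at f = 20%, +67% at f = 40%. Censoring at the last scan also removes follow-up time. With λ = ln 2/8 = 0.0866 per week, mean time is 11.54 weeks, and the mean time since the last 6-week scan is 11.54 − 6/(e^(6λ) − 1) = 2.74 weeks, or 23.7% of the mean. The ratio becomes (1 − 0.237f)/(1 − f): +19% at f = 20% and +51% at f = 40%. At f = 30% it is 0.929/0.70 = 1.33, in line with 13.9/10.5 = 1.32.

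**6. Registration fallback.** Take registration to be IRT enrolment (an assumption), allowed up to 3 days before C1D1 (Protocol Table 1, footnote 8). For enrolment 0, 1, 2 or 3 days before first dose, the formula gives PFS = 1, 0, −1 or −2 days. Table 3 gives 1 day.

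**The case against.** The best defence is that Table 3 is the explicit, row-by-row derivation and a programmer would follow it. Section 6.4.2.3 itself takes disease progression as the event and does not restrict documented progression to imaging in its formula. That stands in part. A reader might infer that 6.4.2.3 never counts marker progression, but it does not say so; the conflict lies in its new-therapy and missed-assessment sentences. The defence does not remove the conflict, because 6.4.2.3 is the analysis-methods section, neither refers to Table 3 nor yields to it, and its new-therapy sentence is unambiguous. Nor can it be read as the RECIST 1.1-alone version: the note under Table 3 derives that PFS from Table 3 as well.

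Other stronger readings also fail:

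- That the two sections start PFS on different dates. Both start at first dose. Registration is only a fallback censoring date, it stands in both texts, and the disagreement is with Table 3.
- That the revision log claims the fallback was corrected. It speaks of the first date, most naturally the start of PFS, and that was corrected.
- That zero or negative PFS biases the result. Such subjects have no post-baseline assessment and leave the risk set before any event under either date. The note on non-evaluable assessments in both sections already sets Day 1.
- That the marker-then-therapy sequence will be common. Protocol 6.1 allows subjects with clinical benefit to remain on treatment after progression, and no frequency is given.

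**Conclusion.** The contradiction holds on the text: one foreseeable path is an event under 5.2.3/Table 3 and censored under the new-therapy sentence of 6.4.2.3. The overstatement of PFS is conditional on that sentence being followed, and its direction is then clear. Its size rests on the share of events affected, which the documents do not give. About 10.5 versus 14 weeks at 30% is an illustration under an assumed 8-week median, not a forecast.

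The registration wording is a tidy-up. PFS is secondary and carries no hypothesis test; the ORR endpoint, the Simon stopping and rejection rules and the sample size are untouched. The point should be settled before database lock, but it does not threaten the trial's main conclusion.

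**What to change.** 1. In SAP 6.4.2.3, delete the repeated censoring rules and refer to 5.2.3/Table 3 as the single PFS rule.
2. Replace the date of registration with the date of first dose as the fallback. Any fallback wording kept in 6.4.2.3 needs the same change as 5.2.3.
3. Replace radiological assessment with disease (or efficacy) assessment in the 5.2.3 text and in the Table 3 row for death after new therapy without prior progression, where the old term also survives.
4. State that the same Table 3 applies to RECIST 1.1-alone PFS, with progression and assessments read under that criterion, so that no separate radiological rule is needed.

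The cost is SAP wording only. No data collection, visit schedule or sample size changes.

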6.5 Analysis of Safety

6.5.1 Dose-Limiting Toxicities

All dose-limiting toxicity (DLT) events, as defined in the DLT criteria in section 2.2.1.1, will be summarized by dose level using DEAS. Details of DLTs will be presented in listings and subject narratives.

6.5.2 Adverse Events

The coding dictionary for this study will be MedDRA v21.1. It will be used to summarize AEs by SOC and PT. AEs will be graded using National Cancer Institute's Common Terminology Criteria for AEs (NCI-CTCAE).

An overview table will include the following details by treatment group and overall:

- Number and percentage of subjects with TEAEs,
- Number and percentage of subjects with causally drug related TEAEs,
- Number and percentage of subjects with serious TEAEs and Astellas upgraded serious TEAE,
- Number and percentage of subjects with serious drug related TEAEs and Astellas upgraded serious drug related TEAE,
- Number and percentage of subjects with TEAEs leading to death
- Number and percentage of subjects with drug-related TEAEs leading to death
- Number and percentage of subjects with TEAEs leading to permanent discontinuation of study drug,
- Number and percentage of subjects with drug related TEAEs leading to permanent discontinuation of study drug, and
- Number and percentage of subjects with grade 3 or higher TEAE
- Number of deaths.

The number and percentage of subjects with TEAEs, as classified by SOC and PT will be summarized by treatment group and overall. Summaries will be provided for:

- TEAEs
- drug related TEAEs,
- serious TEAEs and Astellas upgraded serious TEAE,
- drug related serious TEAEs and drug related Astellas upgraded serious TEAE,
- TEAEs leading to permanent discontinuation of study drug,
- drug related TEAEs leading to permanent discontinuation of study drug,
- TEAEs excluding serious adverse events that equal to or exceed a threshold of 5% in any treatment group, and
- Common TEAEs that equal to or exceed a threshold of 10% in the total group.
- TEAE with CTCAE Grade 3 or higher

The number and percentage of subjects with TEAEs and TEAEs leading to death, as classified by PT only, will be summarized by treatment group and overall.

AE summary tables will include subject counts as opposed to AE counts. If a subject experiences more than one episode of a particular AE, that subject will be counted only once for that event. If a subject has more than one AE that code to the same preferred term, the subject will be counted only once for that preferred term. Similarly, if a subject has more than one AE within a body system, the subject will be counted only once in that body system.

TEAEs and the number and percentage of subjects with TEAEs, as classified by SOC and PT will also be summarized by NCI-CTCAE severity grade and by relationship to study drug. If an adverse event changes in severity grade or relationship, then the subject will be counted only once with the worst severity grade and highest degree of relationship. The adverse event however will be presented in each category they were classified to. If a subject has an event more than once with missing severity grade/relationship and with non-missing severity grade, then the subject will be counted as the highest non-missing grade. If a subject has an event more than once with missing relationship and with non-missing relationship, then the subject will be counted as related. Drug related TEAEs will be presented in a similar way by severity only.

The number and percentage of subjects with treatment-emergent adverse events of special interest (AEoSI), as classified by SOC and PT will also be summarized by treatment group and overall. The list of AEoSI to be summarized may change during the course of the study due to ongoing pharmacovigilance. It will be finalized before the database hard lock.

All AEs, deaths, SAEs and withdrawals due to adverse events will be displayed in listings.

6.5.3 Clinical Laboratory Evaluation

The baseline visit is the last measurement taken prior to initial study drug administration.

Selected quantitative clinical laboratory variables, i.e. hematology, biochemistry, coagulation and urinalysis will be summarized using mean, standard deviation, minimum, maximum and median by cohort and dose level at each visit. Additionally, a within-subject change will be calculated as the post-baseline measurement minus the baseline measurement and summarized in the same way. Changes in laboratory values will be summarized for baseline values versus minimum, maximum and last post-baseline values. Plots of median lab values at each scheduled assessment time by cohort and dose level may be provided for each laboratory parameter.

Frequency tabulations of selected qualitative clinical laboratory variables (i.e. urinalysis) will be presented by cohort and dose level at each visit.

Laboratory results will also be graded using NCI-CTCAE, where possible. Parameters that have criteria available for both low and high values, i.e., hypo- and hyper-, will be summarized for both criteria. The same subject can be counted for both values if the subject has different laboratory values meeting each criterion. NCI-CTCAE grade of laboratory evaluations will be summarized by number and percentage of subjects for each visit. Shift

tables of NCI-CTCAE grade change from baseline to worst post-baseline grade for selected laboratory parameters will also be presented.

The list of laboratory parameters to be summarized may change during the course of the study due to ongoing pharmacovigilance. It will be finalized before the database hard lock.

Laboratory data will be displayed in listings.

6.5.3.1 Liver Safety Assessment

The following potentially clinically significant criteria in liver function tests for Alkaline Phosphatase (ALP), Alanine Transaminase (ALT), total bilirubin, Aspartate Transaminase (AST) and their combinations are defined. The subject's highest value during the investigational period will be used.

Table 5 Potentially Clinically Significant Criteria

Parameter	Criteria
ALT	> 3xULN > 5xULN > 10xULN >20xULN
AST	> 3xULN > 5xULN > 10xULN >20xULN
ALT or AST	> 3xULN > 5xULN > 10xULN >20xULN
Total Bilirubin	> 2xULN
ALP	> 1.5xULN
ALT and/or AST AND Total Bilirubin(*)	(ALT and/or AST > 3xULN) and Total Bilirubin > 2xULN
ALT and/or AST AND Alkaline Phosphatase AND Total Bilirubin(*)	ALT and/or AST > 3xULN AND Alkaline Phosphatase < 2xULN AND Total Bilirubin > 2xULN

* Combination of values measured on the same day or within one calendar day.

The number and percentage of subjects with potentially clinically significant values in liver enzymes and total bilirubin during the investigational period will be presented by cohort and dose level.

6.5.4 Vital Signs

Descriptive statistics will be used to summarize vital sign results and changes from pre-dose on the day of infusion for subjects in the SAF by dose level and time point. Weight and BSA

results and change from baseline will also be summarized with descriptive statistics and listed.

Potentially clinically significant vital signs will be tabulated with summary statistics. The following potentially significant clinically significant criteria are defined for each parameter:

Vital Sign Variable	Criteria
SBP	≥ 180 mmHg AND ≥ 20 mmHg change from baseline
SBP	≤ 80 mmHg
DBP	≥ 105 mmHg AND ≥ 15 mmHg change from baseline
Pulse Rate	≥ 120 bpm AND ≥ 15 bpm change from baseline

Vital signs data will be displayed in listings.

